9.8.3 Treatment Compliance

Study medication tubes will be weighed at each follow-up clinic visit.

Subjects will complete a daily diary recording the date and time of each dose applied, any missed doses, and a comment section should the subjects have a comment, e.g., record potential AEs. Site personnel will review the diaries and use the information to question the subject regarding compliance and AEs and then record appropriate information in source documents and complete Case Report Forms (CRFs). If a subject misses a dose, they should be instructed to return to the

protocol study medication administration schedule (i.e. if subject forgets a dose they should wait until that evening and apply as usual).

Compliance will be assessed by review of the dosing diary. Weight of study medication applied will be measured for reporting purposes. Compliance will be documented in source and in eCRF.

10 STUDY PROCEDURES

10.1 Safety Assessments

The Schedule of Visits and Assessments (see [Section 5](#)) summarizes the clinical procedures to be performed at each visit. Individual clinical procedures are described in detail below. Additional evaluations/testing may be deemed necessary by the PI and/or the Sponsor for reasons related to subject safety.

This study assesses the long-term safety of ARQ-151 cream 0.3%. Safety will be monitored through application site assessments in the clinic using the method of Berger and Bowman, physical examination, clinical laboratory testing, 12-lead ECGs, PHQ-8, C-SSRS and AEs as outlined in the Schedule of Visits and Assessments ([Section 5](#)). If deemed necessary, additional safety assessments will be performed at the discretion of the Investigator.

Screening Visit (Cohort 2)

Within 35 days prior to the first dosing, non ARQ-151-201 subjects will be provided details of study requirements and sign an informed consent. Each subject will undergo psoriatic plaque assessments, a physical examination, vital sign measurements (blood pressure, heart rate, and temperature), PHQ-8, C-SSRS, and laboratory tests: hematology, chemistry, urinalysis and a pregnancy test for female subjects of child bearing potential.

Screening should occur for Cohort 1 subjects if they have completed ARQ-151-201 previously.

All screened subjects will receive a screening number and be entered into the electronic subject tracking system.

Day 1 Visit

At Day 1 (Week 12 of the ARQ-151-201 study or Day 1 for non ARQ-151-201) ARQ-151-201 subjects will be provided details of study requirements and sign an informed consent. Medical history and demographic data, psoriatic plaque assessments (IGA, I-IGA, mPASI and BSA), physical examination, vital sign measurements (blood pressure, heart rate, and temperature), PHQ-8, C-SSRS, laboratory tests: hematology, chemistry, urinalysis and a pregnancy test for female subjects of child bearing potential will be obtained at Week 12 visit of study ARQ-151-201 and will serve as the Day 1 for ARQ-151-201 subjects (Cohort 1). Cohort 2 Day 1 assessments for this long-term safety study (ARQ-151-202) will be completed within 35 days of Screening. The Baseline values for Safety tabulations will be taken from the day that the subject received their first active study drug (across studies ARQ-151-201 and ARQ-151-202). Baseline values for efficacy will be those recorded on Day 1 of Study ARQ-151-201 (Cohort 1) and Day 1 of ARQ-151-202 for non ARQ-151-201 subjects (Cohort 2).

Cohort 2 subjects must meet the required wash out period for any excluded medications and treatments according to [Table 2](#).

All Cohort 1 subjects will retain their Subject ID from the previous study which will be entered into the electronic subject tracking system for this long-term safety study. Cohort 2 subject study numbers will include the 2 digit site number and the three digit subject number will begin with 500.

Scheduled Visits (Day 1 and Visits 1 – 5)

10.1.1 Physical Examination

Physical examinations will be performed as follows:

Day 1, Week 24, and Week 52.

The physical exam will be limited to skin, lungs and heart only.

10.1.2 Vital Signs, Height and Weight

Vital signs will be collected at timepoints noted below:

Blood pressure, heart rate, and temperature will be measured at all study visits.

Height will be collected at Day 1 only.

Weight will be collected at all study visits. Subject to void prior to weight being taken and remove any jackets, outerwear and shoes. Remove any objects of significant weight (i.e. cell phones, wallet, key chains). A 5% weight loss should be reported to the medical monitor.

10.1.3 12-lead ECGs

12-lead ECGs will be performed as follows:

Day 1, Week 24 and Week 52.

ECGs will be performed on subjects after 5 minutes in the supine position. All ECG tracings and readouts will be reviewed by the central reader at the ECG laboratory.

10.1.4 Laboratory Tests

All tests listed below will be performed as follows:

Day 1, Weeks 4, 12, 24, 36, 52.

All tests listed below will be performed according to the Study Events Flow Chart unless otherwise noted. The collection of specimens will be in a non-fasting state. In addition, laboratory safety tests may be performed at various unscheduled timepoints, if deemed necessary by the Investigator.

Hematology

- Hemoglobin
- Hematocrit
- Total and differential leukocyte count
- Red blood cell count with indices and morphology
- Platelet count

Serum Chemistry

- Blood Urea Nitrogen
- Bilirubin (total and direct)
- Alkaline phosphatase
- Aspartate aminotransferase
- Alanine aminotransferase
- Albumin
- Sodium
- Potassium
- Chloride
- Glucose
- Creatinine

Urinalysis

- pH
- Specific gravity
- Protein*
- Glucose
- Ketones
- Bilirubin
- Blood*
- Nitrite*
- Urobilinogen
- Leukocyte esterase*

Additional Tests

- Urine pregnancy test**
(for females of child bearing potential only)

* If urinalysis is positive for protein, blood, nitrite and/or leukocyte esterase, a microscopic examination (for red blood cells, white blood cells, bacteria, casts, and epithelial cells) will be performed.

** At Day 1, Weeks 4, 12, 24, 36 and 52 for FOCBP only

10.1.5 Patient Health Questionnaire depression scale (PHQ-8)

The 8 item PHQ-8 Assessment will be performed as follows:

Day 1, Weeks 4, 12, 24, 36, and 52

Subjects will complete PHQ-8 questionnaire.

A subject with a PHQ-8 score of '15' or above should be referred promptly to a mental health care professional and, if currently applying study drug, consideration be given to discontinuation from study drug.

The PHQ-8

Over the **last 2 weeks**, how often have you been bothered by any of the following problems?
(circle **one** number on each line)

How often during the past 2 weeks were you bothered by...	Not at all	Several days	More than half the days	Nearly every day
1. Little interest or pleasure in doing things	0	1	2	3
2. Feeling down, depressed, or hopeless.....	0	1	2	3
3. Trouble falling or staying asleep, or sleeping too much	0	1	2	3
4. Feeling tired or having little energy.....	0	1	2	3
5. Poor appetite or overeating	0	1	2	3
6. Feeling bad about yourself, or that you are a failure, or have let yourself or your family down.....	0	1	2	3
7. Trouble concentrating on things, such as reading the newspaper or watching television.....	0	1	2	3
8. Moving or speaking so slowly that other people could have noticed. Or the opposite – being so fidgety or restless that you have been moving around a lot more than usual	0	1	2	3

PHQ-8 score is the sum of the responses for the 8 questions.

Five severity categories of depression are defined as follows:

- None – Minimal depression (0 to 4)
- Mild depression (5 to 9)
- Moderate depression (10 to 14)
- Moderately severe depression (15 to 19)
- Severe depression (20 to 24)

10.1.6 Columbia-Suicide Severity Rating Scale (C-SSRS)

C-SSRS Assessments will be performed as follows:

Day 1, Weeks 4, 12, 24, 36, and 52

On all visits, the Since Last Visit version ([Appendix 1](#)) will be used for Cohort 1.

Cohort 2 will use the Baseline/Screening version ([Appendix 2](#)) for Day 1 and Since Last Visit version for all remaining visits.

- Any score greater than 0 in the suicidal ideation score is important and may indicate the need for mental health intervention and consideration be given to discontinuation from study drug. This should result in prompt referral to a mental health professional and/or possibly the emergency room. The Medical Monitor should be contacted.

Clinical study staff that administer the C-SSRS will be trained via the C-SSRS training video. A training certificate for the administer(s) will be on file in the trial master file at the site.

The Investigator must review the completed C-SSRS. A qualified mental health care provider must be available, immediately if needed, to refer the subject for further evaluation.

10.1.7 Local Tolerability Assessments

The Investigator Local Tolerability Assessment will be performed as follows:

Day 1, Weeks 4, 12, 24, 36, and 52

Application site reactions will be graded at the timepoints outlined in the Schedule of Visits and Assessments ([Section 5](#)). Irritation reactions are graded using the scale detailed in the following section ([Berger-1982](#)). Reactions at the site of product application, which may occur post-Day 1 visit, should be differentiated from the preexisting inflammation associated with the subject's psoriasis.

Dermal Response

- 0 = no evidence of irritation
- 1 = minimal erythema, barely perceptible
- 2 = definite erythema, readily visible; minimal edema or minimal papular response
- 3 = erythema and papules
- 4 = definite edema
- 5 = erythema, edema and papules
- 6 = vesicular eruption
- 7 = strong reaction spreading beyond application site

Other Effects

- A = slight glazed appearance
- B = marked glazing
- C = glazing with peeling and cracking
- D = glazing with fissures
- E = film of dried serous exudates
- F = small petechial erosions and/or scabs
- G = no other effects

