9.8.2 Treatment Administration

At the Day 1 visit, subjects will be instructed to apply study medication once daily. All subjects should apply medication each evening at least 15 minutes after showering or bathing (if they take an evening shower/bath) and then not wash areas where ARQ-151 cream has been applied until the following morning. Study medication should be applied at least 20 minutes before going to bed.

Subjects should continue to apply study medication to all active psoriasis lesions including any new plaques that develop during the study. A Body Diagram should be used to record existing and new areas of psoriasis involvement that are subject to treatment.

Psoriasis plaques that have completely resolved, in the opinion of the investigator, do not require continued treatment. If psoriasis plaques appear to resolve at some time between study visits, study medication should continue to be applied until the next scheduled visit. At that visit, the Investigator will perform an assessment and determine whether or not to discontinue treatment.

Study medication will be weighed prior to dispensing at all visits where study medication is dispensed. Study medication, both empty and full tubes, must be returned by subjects at each study visit and will be weighed.

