10.8 Treatment Stopping Rules

For subjects that clear (i.e. have an IGA score of 0 (Clear), an I-IGA (if applicable) of 0 (Clear) **and** an mPASI of 0) treatment may be stopped. The subject will be instructed to document in their diary when they resume treatment with study drug if psoriasis returns. If the subject clears between study visits they should be scheduled for an unscheduled visit for the Investigator to confirm the subject has cleared.

Subjects will call the site when psoriasis returns prior to restarting application of study drug.

If a subject has non-cutaneous adverse events of concern, clinically significant laboratory values or any condition that the investigator determines could possibly be related to the study drug, the Investigator should immediately contact the Medical Monitor to discuss if the subject should be discontinued from the study.

Treatment for any individual subject will be discontinued if the subject experiences:

- A serious adverse event (SAE) or a clinically significant non-serious AE which in the opinion of the Principal Investigator or Medical Monitor warrants discontinuation from the study for that subject's well-being.
- A severe (Grade 3) laboratory abnormality (confirmed by repeat sample and considered related to study drug).
 - See [Appendix 2](#) for details.

Dosing of study drug for an individual subject may be suspended for safety concerns other than those described above, at the discretion of the investigator if he/she feels the subject's safety may be threatened.

A subject with a PHQ-8 score of '15' or above should be referred promptly to a mental health care professional and consideration be given to discontinuation from study drug.

A subject that is experiencing suicidal ideation and behavior should be referred immediately to a qualified mental health care provider and consideration given to discontinuation from study drug.

As noted above, study treatment must be discontinued immediately in the event of a female subject's pregnancy.

Treatment should be interrupted:

- If a subject develops an application site reaction with the clinical appearance of an 'irritation reaction', and with a severity of a Dermal Response Score of 5 (erythema, edema and papules) or greater on the scale of Berger and Bowman. Treatment can be interrupted for up to one week and may then be resumed if the reaction has, in the opinion of the Investigator, adequately resolved.

Treatment should be discontinued:

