11.1.3 Subjects to Analyze

All analyses will be performed using the Safety Population which includes all subjects who are enrolled and received at least one confirmed dose of ARQ-151 cream 0.15% or ARQ-151 cream 0.3% study medication either in the Phase 2b Study (ARQ-151-201) or this extension study (ARQ-151-202). The number of patients included in the Safety Population will be summarized.

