11.2.3 Clinical Laboratory Results and Vital Signs/Weight Measurements

Vital signs will be tabulated by scheduled study visit.

Routine blood chemistries and urinalysis will be obtained throughout the study and the results summarized by parameter and at scheduled study visits.

All clinical laboratory results and vital signs measurements and their change from baseline will be summarized along with timepoint of collection.

A shift table describing out-of-normal range shifts will be provided for clinical laboratory results.

A shift table will identify subjects who gain or lose >5% body weight over the course of the study.

11.2.4 ECG:

ECGs will be tabulated by scheduled study visit.

11.2.5 Local Tolerance Assessments:

For the Investigator's assessment the numeric application site reaction scores will be summarized individually by using number and percentage of subjects by visit.

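### The by-visit local tolerability table mixes subjects applying the cream with cleared subjects who have stopped it, so it can understate the on-drug reaction rate and confound comparisons between visits

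*Protocol*

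**What the plan says.** **Scoring.** Protocol section 10.1.7 schedules the Berger and Bowman score at "Day 1, Weeks 4, 12, 24, 36, and 52". It adds that "Application site reactions will be graded at the timepoints outlined in the Schedule of Visits and Assessments", and the schedule in section 5 marks it at those same clinic visits. It is not scheduled at Screening or at the phone visits. Neither section exempts subjects who are off drug or provides a not-applicable entry; the lowest dermal grade is 0, no irritation. What is graded is the effect of the product: "Reactions at the site of product application, which may occur post-Day 1 visit, should be differentiated from the preexisting inflammation" of the psoriasis.

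**Stopping.** Section 9.8.2 says that "Psoriasis plaques that have completely resolved, in the opinion of the investigator, do not require continued treatment". For subjects clear on IGA, on I-IGA where applicable, and on mPASI, section 10.8 says that "treatment may be stopped. The subject will be instructed to document in their diary when they resume treatment with study drug if psoriasis returns". Section 10.5 likewise has such subjects remain in the study off drug. Section 9.1 admits subjects with as little as 0% BSA.

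**Analysis.** Section 11.1.3: "All analyses will be performed using the Safety Population which includes all subjects who are enrolled and received at least one confirmed dose" of active cream, in either the parent study or this one. Section 11.2.5: "the numeric application site reaction scores will be summarized individually by using number and percentage of subjects by visit". Section 11.1 adds, for percentages in general, that the denominator is whatever number of subjects suits the analysis.

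**The concern.** A local tolerability percentage for a topical product is normally read as the proportion of users who show a reaction. Here the table would also count people with no product on the skin as having tolerated it. Being off drug is a planned state: the time from stopping to restarting is a secondary endpoint (8.2.2, 11.3). After Week 12 the clinic visits are 12, 12 and 16 weeks apart, so a subject confirmed clear at one visit may be long off drug by the next.

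The AE tables do not fully cover the gap. Under section 10.6.1 an application site reaction is an AE only if it requires intervention, or suspension or discontinuation of the drug. The interruption rule in 10.8 begins at a Dermal Response of 5. Lower-grade reactions that need no action may therefore be visible only in the 11.2.5 table. Section 8.2.1 lists application site assessment among the measures by which the primary safety endpoint is monitored.

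**Working it through.** **No figure to reproduce.** The protocol states no reaction rate, off-drug share, power or precision. The only planned number is about 300 (Cohort 1) plus up to about 100 (Cohort 2), so N is at most about 400 (11.1.2). The reaction rates and off-drug shares below are assumptions, shown over a range.

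**Formula.** Let r be the reaction rate among subjects applying the cream, r0 the rate among those off drug, and f the off-drug share of subjects assessed at the visit. Then

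observed = (1 − f) × r + f × r0,

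and the shortfall from r is f × (r − r0). It is positive whenever r0 is below r. With r0 = 0, observed = (1 − f) × r and the relative understatement is exactly f.

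**Size at one visit, r0 = 0:**

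| Assumed r | f = 10% | f = 20% | f = 30% | f = 40% |
|---|---|---|---|---|
| 2% | 1.8% | 1.6% | 1.4% | 1.2% |
| 5% | 4.5% | 4.0% | 3.5% | 3.0% |
| 10% | 9.0% | 8.0% | 7.0% | 6.0% |

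For scale, at r = 5% and N = 400 the standard error is √(0.05 × 0.95 / 400) = 1.09 percentage points. The shift is f × 5 points: 0.5 points at f = 10% and 2.0 points at f = 40%.

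**Comparison between visits.** Hold r at 5% and vary only f over Weeks 4, 12, 24, 36 and 52:

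| Assumed f by visit | Observed % | Apparent trend |
|---|---|---|
| 0, 5, 10, 20, 30% | 5.0, 4.75, 4.5, 4.0, 3.5 | improvement |
| 10% throughout | 4.5 at each visit | none |
| 30, 20, 15, 10, 5% | 3.5, 4.0, 4.25, 4.5, 4.75 | worsening |

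The falling pattern is possible. Section 11.3 counts treatment-free days for previously active rollovers from their last treatment begun in the parent study, so some may start off drug and restart later. The sign of any artefact over time is therefore undetermined.

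**After a split.** The on-drug percentage equals r at every visit, whatever f is. If all 400 were assessed, the on-drug denominator would be 400 × (1 − f): 360, 320, 280 or 240 at f = 10%, 20%, 30% or 40%.

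**The case against.** The strongest reply is that a per-visit denominator is routine SAP content. Section 11.1 calls the protocol methods a summary and allows a suitable denominator, and 11.1.3 fixes a population without fixing who is counted at each visit. That sentence does leave room for an on-drug denominator, but it does not create one. The specific text in 11.1.3 covers all analyses and defines membership by a single dose ever, and 11.2.5 adds no restriction. The protocol does condition on current use elsewhere: the PHQ-8 rule in 10.1.5 distinguishes subjects currently applying drug. Section 10.1.7 does not.

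Several further objections stand and limit the point:

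- **Zeros are an inference.** No rule says how an off-drug subject is scored. Zero is likely, because IGA 0 excludes erythema and thickening, but a not-applicable entry is neither provided nor ruled out.
- **The off-drug share may be small.** Stopping under 10.8 needs all applicable scores at clear. Under 9.8.2, treatment of plaques that seem to resolve between visits continues until the investigator assesses them. Palms and soles are treated but not scored (10.2.1), so clear does not always mean off drug.
- **A false improvement over time does not follow.** A reader might infer one. It would need an off-drug share that rises across visits; the documents give none, and rollovers may start off drug and relapse.
- **The primary analyses are not biased by this.** A reader might infer otherwise from 8.2.1, but the two planned primary analyses are TEAEs and SAEs, and neither uses this denominator.
- **An on-drug table has its own selection.** It describes subjects who have not cleared, whose residual inflammation must be told apart from irritation. The all-subject table answers a legitimate question about the stop-and-restart regimen. This argues against replacing it, not against adding a split.

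**Conclusion.** The point holds in a limited form. As the protocol is written, cleared subjects who have stopped the cream are scheduled for scoring and belong to the population in which the percentages are calculated. If they score 0, each post-baseline percentage understates the on-drug reaction rate by the relative amount f. The illustrative 10% to 40% for f has no source in the documents. Comparisons between visits mix any change in tolerability with change in f, and the direction of that distortion cannot be told in advance.

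The table is descriptive (11.2 plans no inferential statistics on safety), and counts of subjects with a reaction are not diluted. This is a worthwhile correction to a secondary safety display. It matters chiefly because milder reactions may be reported nowhere else.

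**What to change.** In section 11.2.5:

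1. Keep the all-subject by-visit table.
2. Add the same table for the post-baseline visits, split by on-drug and off-drug status at the visit. Derive status from diary-recorded applications within a window before the visit, with its length fixed in advance.
3. Count subjects whose cream was interrupted because of a reaction with the on-drug group; otherwise the split would remove the very reactions it is meant to show.
4. Draw by-visit tolerability conclusions from the on-drug rows.

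Section 10.1.7 should also say whether an off-drug subject is graded or marked not applicable, so that sites record the same thing.

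**Cost.** One derived flag and a few lines of wording. The diary already records each application and any restart (9.8.3, 10.8), so no new data are needed. On-drug denominators will be smaller, possibly most at late visits, and the reported rate may be slightly less favourable. The on-drug rows describe subjects who have not cleared, which the table footnote should state.

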10.1.8 Adverse Events

Adverse events (AEs) will be collected beginning at informed consent and assessed as follows:

Day 1, Weeks 4, 12, 24, 36, and 52

Any treatment emergent AEs will be followed in the clinic for up to one month at the Investigator's discretion until resolved or otherwise judged as clinically stable.

A psoriasis flare will be considered an AE in this study. For further details on Adverse Events please see [Section 10.6](#).

